#### *4.3.2 Usual care group*

Those in the usual care group will complete all the same study assessments as those in the intervention group. They will not receive any specific dietary advice, but they will be allowed to voluntary seek dietary advice from a registered dietitian, use resources at the Integrative Oncology Center, attend cooking classes, etc. There is currently no standard of care regarding nutritional prescriptions during chemotherapy. We will emphasize how their data are indispensable in understanding the nutritional habits and preferences of patients undergoing chemotherapy, and how these data will be used to optimize nutritional interventions in future studies. At the end of the 8-week intervention, the participants in the usual care group will be provided the intervention materials *gratis*, including one-week of Mediterranean Diet food and education materials.

### 4.4 Study outcomes/endpoints

#### *4.4.1 Aim 1: Feasibility and adherence*

The primary aim of our study is to assess feasibility of implementing a Mediterranean Diet intervention. Feasibility will be determined by our ability to recruit participants to the study and have them complete the intervention. Our goal is that at least 70% of participants in each group complete the 8-week intervention including 8-week assessments.

1. 14-item Mediterranean Diet assessment: As part of Aim 1, we will assess the adherence of the participants to the diet. Adherence will be assessed primarily from the 14-item Mediterranean Diet assessment tool that is used commonly in the literature, mostly for epidemiological studies but also for clinical trials. We will ask participants to report their dietary habits over the last week. Questions include: ‘How many servings of fruit do you consume per day?’, ‘How many sweet or carbonated beverages do you consume per week?’, and ‘How much olive oil do you consume on a given day?’ We will deem a participant adherent if they show an improvement in score of at least 1 point from baseline to 4 weeks and baseline to 8 weeks. This cut-off has been established in the literature to be clinically relevant.
2. 3-Day food record: We will further assess dietary habits using a 3-day food record at baseline (before randomization), week 4, and week 8. For this record, participants will write down what they ate, how much, and at what time for one weekend day and two week days (preferably consecutive, but not necessarily). The 3-day food record will give us a more nuanced snapshot of the foods the participants were consuming leading up to the study, as well as the foods that they consumed during the study period. It also includes timing of nutrient ingestion, which will provide insight into patients’ nutrient habits during chemotherapy and circadian rhythm. The food record will be completed at home, preferably in real-time. We will provide participants with a paper food record; there are also apps that participants can use on their phone to track food intake (e.g., Chonometer), though we will ask participants to transcribe the data to the questionnaire to submit to us. We will use NDSR software (Regents of the University of Minnesota, Minneapolis, MN) or a similar program to analyze dietary intake for macro- and micronutrients. The patient-reported 3-day food record was selected to assess diet instead of a 24-hour food recall, food frequency questionnaire, or weighed food record for this situation because 1) food intake can be entered in real time and does not rely on recall, and memories are not always accurate; 2) food frequency questionnaires inquire about more general meal patterns (e.g., How often do you eat fish?), and food intake during the cancer experience can be much different than “normal” and change rapidly over the course of

chemotherapy; the 3-day food record will be more accurate; 3) it is burdensome and sometimes not practical to weigh food before it is consumed; and 4) being participant-completed and not guided by an interviewer, participants might feel less self-conscious about eating “junk food” and be more honest. Additionally, food records tend to have higher correlations with blood carotenoid biomarkers than 24-hour recalls, diet history, and food frequency questionnaires.

#### *4.4.2 Aim 2: Patient-reported fatigue measures*

Aim 2 of our study is to assess the effects of the Mediterranean Diet on cancer-related fatigue, as assessed using the FACIT-F. Patients will complete this instrument at baseline, 4 weeks, and 8 weeks.

1. Functional Assessment of Chronic Illness-Fatigue (FACIT-F) questionnaire: The FACIT-F is a 40-item, validated, commonly used measure of fatigue that is comprised of 5 subscales: physical well-being, social well-being, emotional well-being, functional well-being, and fatigue-specific well-being. It captures fatigue in these categories over the last 7 days. The 13-item FACIT-F fatigue subscale will be used as the primary aim.

#### *4.4.3 Mechanistic aims: Metabolic measures*

Blood will be collected at the Wilmot Cancer Institute, Pluta Cancer Center, a UR Lab Patient Service Center, or medical office and a trained study staff member will transport the samples to our facility. Participants will be requested to fast overnight (at least 8 hours) before the blood draw. The location will be selected to minimize subject burden and if possible we will perform blood draws at the same time as a regularly scheduled medical blood draws. If a participant is not fasted at the time of the blood draw, blood will still be drawn and a note will be made. The blood draw can occur the same day as their chemotherapy infusion, or at another time.

Approximately 40 mL of blood (around 3 tablespoons) will be drawn at baseline (week 0); approximately 40 mL will be drawn at 4 weeks, and approximately 20 mL of blood will be drawn at 8 weeks. This is a total of approximately 100 mL of blood over 9 weeks. We will collect the following:

1. At baseline and 4 weeks, we will collect blood in two light-green-top (sodium heparin) tubes (10 mL each, 20 mL total). These tubes will be inverted 8-10 times and stored at room temperature. They will be used the same day for T cell extraction and real-time metabolic assays for basal respiration, maximal oxygen consumption, etc.
2. At baseline, 4 weeks, and 8 weeks, we will collect blood in two tubes (red top and/or serum separator); these will be sent to UR Labs for analysis and/or brought to the CCPL.

Live-cell metabolic assays will be conducted by [name] or trained study staff. First, T cells will be isolated using established procedures, and plated on a Seahorse 48-well plate. The Extracellular Flux XF instrument (also known as the Seahorse) in the Flow Cytometry Core will be used to perform a standard Mitochondrial Stress Test. This test involves injecting metabolic inhibitors onto the cells *ex vivo* to evaluate oxygen consumption rate and extracellular acidification rate (ECAR, i.e., change in pH), which provides detailed information regarding mitochondrial function. Other metabolic measures will be assessed either by UR Labs or in the CCPL.

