### 2.1.6 Mitochondrial dysfunction as a contributor to cancer-related fatigue

Mitochondrial dysfunction is increasingly recognized as a major contributor to fatigue due to mitochondria's essential role in energy production, generation and regulation of reactive oxygen species, and other physiological processes. Mitochondria are inadvertent targets of chemotherapy (especially doxorubicin and oxaliplatin); chemotherapy causes damage to the mitochondrial structure and function, as well as its DNA. Further, mtDNA is more susceptible to mutations and has poorer repair mechanisms than nuclear DNA, likely exposing it to worse damage from chemotherapy. Indeed, reduction of mtDNA content in peripheral blood cells was significantly greater among those with worsening of cancer-related fatigue compared to those without fatigue in patients with early-stage breast cancer undergoing

chemotherapy. There have been eight studies to our knowledge probing mitochondrial function in the context of cancer-related fatigue including our own. Six of these studies looked at associations between mitochondrial function and fatigue during treatment from radiotherapy, one enrolled patients initiating anthracycline- or taxane-based chemotherapy, and ours recruited survivors of breast cancer who underwent a variety of antineoplastic treatments. Collectively, these studies show that fatigue is associated with less mtDNA, downregulated mitochondrial gene expression, and less complex III-linked respiration but no changes in the activity of mitochondrial oxidative phosphorylation complex enzymes, all in circulating blood cells. Our study in survivorship showed that lower mitochondrial gene expression was associated with greater subsequent improvements in fatigue over the course of study. However, a major gap in the literature is that **mitochondrial function (i.e., efficiency of ATP production) and energy metabolism has not been thoroughly characterized in the context of cancer-related fatigue, especially as derived from chemotherapy treatment.**

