## 2.3 Innovation

A major gap in the literature is whether implementing a healthy dietary pattern during chemotherapy can reduce symptom and side effect burden. This is one of the first randomized controlled trials to implement a dietary change during chemotherapy to address supportive care outcomes. It is the first to provide food based on the Mediterranean Diet during chemotherapy, and it is the first diet-based intervention during chemotherapy to look at cancer-related fatigue as the primary outcome.

One of the reasons that there are not effective preventative strategies or treatments for cancer-related fatigue is that its etiology is largely not understood. This study will use a powerful metabolic assay (respiration of freshly isolated human T cells) as well as a battery of standard metabolic assays (e.g., fasting blood glucose, insulin) to describe the effects of chemotherapy on metabolic function in unprecedented detail. These data will be valuable in drawing associations between metabolic health and patient-reported symptoms regardless of adherence to the Mediterranean Diet. These data will be able to inform the optimization of this dietary intervention for a follow-on randomized controlled trial.

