### 8.2.7 Schedule of assessments

Baseline assessments will optimally be collected before the first infusion of chemotherapy, though assessments will not delay chemotherapy. Baseline assessments after chemotherapy is initiated is permissible as long as the patient has at least 6 more weeks of chemotherapy. 4-Week assessments will occur approximately during week 4 (during week 3-5); 8-week assessments will occur approximately during week 8, the last week of the intervention (week 7-9). However, this may be adjusted to accommodate factors such as the participant or researcher's schedule. Because of the immediate and transient effects that chemotherapy has on fatigue, we will aim to have assessments at least 3 days after an infusion. Optimally, the post-intervention assessments will occur during the last week of the intervention, while the participant is still on the diet, so that we can probe metabolic markers that may change quickly after cessation of the diet. **Table 3** describes two common chemotherapy regimens, but others exist and we will work around clinic activities to collect assessments.

Study Week	0	1	2	3	4	5	6	7	8
Study activities	Consent, Baseline assessments				4-week assessments				8-week assessments
Infusion number (for patients on biweekly regimens)		1		2		3		4	
Infusion number (for patients on weekly regimens)		1	2	3	4	5	6	7	8
Infusion number (for patients on an every 4-week regimen)		1				2			
Infusion number (for patients on an every 3-week regimen)		1			2			3	

**Table 3.** Schedule of chemotherapy infusions and study activities for two example chemotherapy regimens.

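### Study blood may be drawn on an infusion day, before or after the infusion, and baseline may follow the first infusion; the biomarker analysis accounts for neither

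*Combined protocol and SAP*

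**What the plan says.** **Timing of blood.** Section 4.4.3 says of the study sample: "The blood draw can occur the same day as their chemotherapy infusion, or at another time". It also says "if possible we will perform blood draws at the same time as a regularly scheduled medical blood draws". It sets no order between sample and infusion. A non-fasting draw is to be noted, but there is no matching note for time since infusion.

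**Timing of assessments.** Section 8.2.7 says "we will aim to have assessments at least 3 days after an infusion", and gives as its reason: "Because of the immediate and transient effects that chemotherapy has on fatigue". Table 4 in section 8.2.8 lists the blood draw among the study assessments, so on its face this aim covers blood. The 4-week visit may fall in weeks 3 to 5 and can be moved further for scheduling reasons. Section 17.1 keeps assessments at their planned time when chemotherapy is delayed.

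**Timing of baseline.** Section 8.2.7 first states a preference: "Baseline assessments will optimally be collected before the first infusion of chemotherapy, though assessments will not delay chemotherapy". It then allows: "Baseline assessments after chemotherapy is initiated is permissible as long as the patient has at least 6 more weeks of chemotherapy".

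**Purpose and analysis.** Section 2.1.6 says "Mitochondria are inadvertent targets of chemotherapy". Section 2.3 says the assays will be used "to describe the effects of chemotherapy on metabolic function in unprecedented detail". Section 17.4.3 specifies ANCOVA at 4 or 8 weeks adjusted for the baseline value, plus longitudinal models. It has no term for time since infusion or for chemotherapy begun before baseline.

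**The concern.** The protocol itself names mitochondria as a target of chemotherapy, so time since the last infusion may plausibly affect what the T-cell assay reads. As written, one participant's week-4 sample can be taken hours after an infusion and another's more than three weeks after. Staff following section 4.4.3 could draw after the infusion; staff following section 8.2.7 would try not to. The overlap is foreseeable: Table 3 places an infusion in week 4 for the weekly and every-3-week regimens, and study draws are to be combined with clinical draws where possible.

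A badly timed T-cell sample cannot be made good. The heparin tubes are drawn only at baseline and week 4, so the hypotheses on ATP turnover, spare respiratory capacity and proton leak have one follow-up sample each. The serum markers are better placed because they are drawn again at week 8.

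A participant whose baseline follows the first infusion cannot show a change from before to during chemotherapy. If the diet proves infeasible, section 4.6 falls back on longitudinal correlations of fatigue with diet and metabolic measures, and randomisation does not protect those.

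**Working it through.** **1. Interval from last infusion to week-4 draw.** Inputs: infusion weeks from Table 3 and the week 3 to 5 window in section 8.2.7. Assume each infusion falls on the first day of its marked week, and count the infusion day as day 0.

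| Regimen | Infusion weeks up to week 5 | Draw in week 3 | Draw in week 4 | Draw in week 5 | Range |
|---|---|---|---|---|---|
| Weekly | 1, 2, 3, 4, 5 | 0-6 | 0-6 | 0-6 | 0-6 days |
| Every 2 weeks | 1, 3, 5 | 0-6 | 7-13 | 0-6 | 0-13 days |
| Every 3 weeks | 1, 4 | 14-20 | 0-6 | 7-13 | 0-20 days |
| Every 4 weeks | 1, 5 | 14-20 | 21-27 | 0-6 | 0-27 days |

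The first randomisation stratum combines weekly, 2-weekly and 4-weekly regimens, so it spans the full 0 to 27 days. Stratification balances planned regimen frequency between arms; it does not fix the interval.

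**2. Are the two sections compatible?** A sample taken on an infusion day but before the infusion is 7, 14, 21 or 28 days after the previous one in these regimens, all at least 3 days. A sample taken after that day's infusion is at day 0 and misses the aim. The sections can therefore be reconciled, but the present wording permits both cases.

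**3. The plan's own power figure.** Section 17.1 gives 80% power for FACIT-F with 33 evaluable participants (22:11), effect 0.75 SD, correlation 0.50 and two-sided alpha 0.15.

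- ANCOVA residual SD = √(1 − 0.50²) = 0.866.
- Standard error = 0.866 × √(1/22 + 1/11) = 0.320.
- 0.75 / 0.320 = 2.345. Subtracting 1.440 leaves 0.906, so power is 81.7% by the normal approximation.
- The noncentral t with 30 degrees of freedom gives 80.6%.

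The figure is reproduced. The plan gives no power for any blood measure.

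**4. Illustration for a biomarker.** The documents give no biomarker SD and no size for an acute effect. Assume a biomarker with the FACIT-F design values. Let a share f of week-4 draws be post-infusion, each shifted by d SD, with the same f in both arms. The residual variance is then 0.75 + f(1 − f)d².

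| d | f | Residual SD | Power (t) |
|---|---|---|---|
| 0 | – | 0.866 | 80.6% |
| 0.5 | 25% | 0.893 | 78.7% |
| 0.5 | 50% | 0.901 | 78.1% |
| 1.0 | 25% | 0.968 | 73.3% |
| 1.0 | 50% | 1.000 | 71.1% |

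If baseline samples are shifted independently in the same way (d = 1.0, f = 50%), power is 69.5%.

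**5. Bias in the arm comparison.** With d = 1.0, f = 50% in both arms and no diet effect, 20,000 simulated trials gave a mean arm difference of 0.004 SD and a type I error of 14.5% against the nominal 15%. There is no bias when timing is the same in both arms.

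Bias equals d times the difference in f between arms. With a systematic 60% versus 40% and d = 1.0, it is 1.0 × 0.20 = 0.20 SD, and simulated type I error rises to 20.5%.

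By chance alone, the difference in f has standard error √[f(1 − f)(1/22 + 1/11)], which is 0.16 at f = 25% and 0.18 at f = 50%. A 20-point gap is thus little more than one standard error. Averaged over trials, that chance imbalance is part of the variance in step 4; in a single trial it can still move the estimate.

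**The case against.** The strongest reply is that the plan is pragmatic and already guards the comparison that matters.

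- **The 3-day statement is an aim, not a rule, and its stated reason is fatigue.** This stands. A reader might infer that section 4.4.3 breaks a 3-day rule. It does not: a same-day draw before the infusion can meet the aim. The fault is that the order is left open.
- **Randomisation protects the arm comparison.** This stands. A reader might infer that chemotherapy effects are confounded with diet. Both arms share the same timing rules, randomisation is stratified by regimen frequency, and ANCOVA adjusts for baseline. Systematic bias would need timing to differ by arm. That is possible in an open-label trial with flexible visits, but nothing in the documents shows it.
- **Other adjustments exist.** Section 4.4.4 promises to account for clinical factors, and section 17.2 adds covariates found imbalanced at baseline. Neither names draw timing, and a baseline check cannot detect imbalance in week-4 timing. This stands only in part.
- **Late baselines are an open choice.** Section 5 asks only for at least 6 weeks of chemotherapy remaining, and section 1 speaks of changes during chemotherapy, which an on-treatment baseline can serve. A reader might infer that late baselines understate the chemotherapy effect by some calculable fraction. The documents give neither the share of late baselines nor the effect already present at that point, and section 17.4.3 defines no estimate of change from before to during chemotherapy.
- **The outcomes are mechanistic.** Section 17.4.4 says secondary and exploratory analyses will be read with great caution. That limits the consequence but does not restore a poorly timed sample.

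**Conclusion.** The point holds as one of unreconciled wording and unmeasured variation. Infusion-day samples may be taken before or after the infusion, baseline may follow the first infusion, and the biomarker analysis uses neither fact. Under Table 3 and the week 3 to 5 window, the interval can be 0 to 20 days on an every-3-week regimen and 0 to 27 days on an every-4-week regimen; dose delays could lengthen it.

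For the randomised biomarker comparison, the expected cost is added noise and chance imbalance. Under the assumptions in the working, power would fall from 80.6% to about 78-79% for a 0.5 SD acute shift and to about 71-73% for a 1.0 SD shift. These figures are illustrative; the true size cannot be obtained from the documents. Within-patient changes and correlations are more exposed, because they can carry acute or earlier chemotherapy effects. The feasibility aim and the FACIT-F power calculation are not affected. The change is worth making because it is cheap and the T-cell assay has only one follow-up sample.

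**What to change.** 1. **Sections 4.4.3 and 8.2.7:** reconcile them so that a research sample on an infusion day is taken before that day's infusion. This concerns research sampling only and does not change treatment.
2. **Data collection:** record the date and time of each draw, the date of the last infusion, and whether baseline preceded the first infusion.
3. **Section 17.4.3, models:** add the regimen stratum and a yes/no term for chemotherapy started before baseline.
4. **Section 17.4.3, sensitivity analysis:** repeat the biomarker comparison without samples drawn within 3 days after an infusion, or adjust for days since infusion.
5. **Descriptive reporting:** report any change from before to during chemotherapy only in participants with a pre-chemotherapy baseline.

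The cost is wording, a few recorded dates and times, and two model terms. Section 8.2.2 already has the team extracting treatment details from the medical record, so infusion dates can be collected the same way. With 33 evaluable participants, the two terms reduce the ANCOVA residual degrees of freedom from 30 to 28. The descriptive estimate will rest on a smaller subset, as will the sensitivity analysis if samples are excluded.

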#### 4.4.4 Exploratory aims and other symptoms and clinical factors

In order to assess the variation in fatigue over the course of a chemotherapy cycle, we will assess average fatigue at the end of each day using a single-item question on a daily diary.

To obtain more precise estimates on the effects of the Mediterranean Diet on cancer-related fatigue and metabolism we will account for several behavioral and clinical factors. For example, several patient-reported outcomes tend to be associated with fatigue (e.g., depression) and we will adjust for these potential factors in our analyses.

1. Aerobics Center Longitudinal Study (ACLS) physical activity questionnaire: The ACLS captures current physical activity and exercise, including walking, climbing stairs, and weight training. We will use this questionnaire to estimate the energy that each participant expends per week on physical activity.
2. Symptom Inventory (SI): The symptom inventory (modified from the MD Anderson Symptom Inventory) includes 19 items that are common in the cancer experience (e.g., pain, distress, lack of appetite, numbness and tingling, fatigue), as well as 8 items related to how much these symptoms interfere with activities of daily living and quality of life. As many symptoms often correlate with each other including fatigue (i.e., symptom clustering), it is important to capture the change in many symptoms from baseline to post-intervention. Exploratory analyses will probe whether adherence to the diet or high consumption of any dietary component correlates with the change in any of these symptoms over time.
3. Brief Fatigue Inventory (BFI): The BFI is a 10-item fatigue questionnaire that is also validated and commonly used. It captures fatigue *now* as well as the usual and worst in the last 24 h. It also includes 6 single-item questions regarding how fatigue has interfered with general activity, mood, work, etc.
4. FACT-Cog: The FACT-Cog is a 41-item questionnaire designed to assess cognitive challenges identified by patients with cancer.
5. Brief Pain Inventory: The Brief Pain Inventory (BPI)-Short Form is a 15-item questionnaire designed to assess the severity of pain and its impact on functioning.
6. Insomnia Severity Index (ISI): The Insomnia Severity Index (ISI) is a brief 7-item questionnaire that was designed to assess the severity of both nighttime and daytime components of insomnia.

Some study data (e.g., questionnaires) will be collected electronically using REDCap software. REDCap is a secure, web-based application for building and managing online surveys and databases and is made available through the CTSI. REDCap will be used to send a secured web link to each study subject, and a built-in scheduling function will allow for re-contact at a pre-specified time to remind subjects to complete the questionnaires if needed. All data forms will be checked immediately by the REDCap system as they are being completed by the study subject to ensure completeness (i.e., that no question was skipped unintentionally), and a pop-up message feature will be used to encourage a response. For participants who prefer paper-based questionnaires, a paper version will be provided for them to complete and return to the study staff in person or in a postage-paid envelope. In this case, a study staff member will enter the responses into the REDCap database.

There are a total of 11 questionnaires and survey assessments that will be completed. The on-study form will be completed at baseline only; the daily diary will be completed every day; the others will be completed at baseline, 4 weeks, and 8 weeks.

- On study (demographics and clinical characteristics; baseline only)
- FACIT-F (fatigue)

- Daily diary (single-item fatigue question)
- 14-item Mediterranean Diet assessment
- 3-day food record
- ACLS (activity)
- Symptom inventory
- BFI (fatigue)
- FACT-Cog (cognition)
- BPI (pain)
- ISI (sleep)

The daily diary will take about 10 seconds each day and the other questionnaires should take approximately 30-45 minutes total to complete.

